Study Design and Methodology:	This will be a nonrandomized, open-label, pilot, observational, phase IV study to evaluate the compliance with and perceptions of treatment, as w as HRQOL in surgically resected melanoma patients undergoing HDI or PEG IFN therapy. The study will consist of a pretreatment (screening) phase, an induction phase, a maintenance phase, and an end-of-study (EG assessment.  Pretreatment/Screening							
	All patients will undergo a standard medical screening within 28 days of study of the first administration of HDI or PEG IFN.							
	Induction Phase							

	All enrolled patients will be offered HDI or PEG IFN and, after discussion with their treating physician, will initiate the therapy of their choice. Suggested dosing per package insert is as follows, but can be altered per institutional guidelines.					
	HDI: 20 million IU/m  as an intravenous (IV) infusion over 20 minutes, 5 consecutive days per week for 4 weeks					
	or PEG IFN: 6 mcg/kg/week subcutaneously (SC) for 8 doses					
	Patients will complete the CCSQ and evaluate the treatment-related side effects that may impact their HRQOL using the FACT-BRM at specified time points during the Induction Phase.  Maintenance Phase					
	During the Maintenance Phase, patients will receive:					
	HDI: 10 million IU/m  as an SC injection 3 times per week for 48 weeks					
	or PEG IFN: 3 mcg/kg/week SC for up to 5 years (only the first year of therapy will be evaluated in this study)					
	This is again the suggested dosing per package insert, and can be altered per institutional guidelines.					
	As in the Induction Phase, patients will complete the CCSQ and FACT-BRM evaluations at specified time points.					
	End-of-Study Assessment					
	All patients who receive HDI or PEG IFN will be requested to return for an EOS visit within 21 days of discontinuation of study treatment. Final diary collection, safety assessments, treatment perceptions and HRQOL evaluations will be conducted at this visit.					
	Safety assessments will be conducted during the study via clinical laboratory tests and adverse event (AE) monitoring.					
Inclusion Criteria:	To be eligible for enrollment in this study, each of the following criteria must be satisfied with a "YES" answer (unless not applicable):					
	1. Patient is a male or female at least 18 years of age					
	2. Patient has had surgically resected melanoma and plans to receive					

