#### 5.4 Management of Clinical Supplies

Patients will receive commercially available product.

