#### 5.4.1 Treatment Discontinuation and Premature Patient Withdrawal

The investigator may at any time determine that a patient should no longer receive treatment with HDI or PEG IFN for reasons related to patient safety or for other reasons. If a patient's treatment with interferon is permanently discontinued, all study procedures will also be discontinued. All data obtained prior to treatment discontinuation will be included in the analysis set.

Patients may voluntarily withdraw from the study for any reason at any time. They may be considered withdrawn if they state an intention to withdraw, or fail to return for visits, or become lost to follow up for any other reason.

If premature withdrawal occurs for any reason, the investigator must determine the primary reason for a patient's premature withdrawal from the study and record this information on the Study Completion case report form (CRF). Patients who are prematurely withdrawn from the study will not be replaced.

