- j Patients will be instructed to record details on the receipt of HDI in the drug administration diary and will return the diary to the site at the subsequent visit. These diaries will capture the onset of AEs in relationship to the day of drug administration.

Patients should be seen for all visits on the designated day or as close as possible to the designated day. Please note that the  $\pm 1$  week interval in the Maintenance Phase of the study is proposed as a guide. Visits falling outside this window should not lead to automatic patient discontinuation.

All data obtained from the assessments listed in the schedule of events must be supported in the patient's source documentation.

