#### 6.8 Treatment Compliance

Patients will complete drug administration diaries to track compliance with the recommended dosing schedule. These diaries will also capture the onset of AEs in relationship to the day of drug administration. The diaries will be returned to the Investigator at the subsequent visit.

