#### 9.1 Compliance

Compliance for HDI and PEG IFN will be analyzed by comparing the percentage of doses taken (as recorded in the diary) over the treatment period as prescribed by the physician.

Analysis of this primary endpoint is described on pages 22-23.

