Data Analysis -REVISED JULY 2023

Due to the study's pilot study design, sample size was not calculated formally. For both primary and secondary outcomes, descriptive data are presented (i.e., medians and ranges for continuous data, frequencies and percentages for categorical data).

Although the original data plan called for exploratory mixed randomized-repeated measures analysis of variance (ANOVA) to be conducted for the primary and two secondary outcomes, the pattern of missing data across patients at the designated time points was too prevalent (and appeared not to be missing at random) to ensure robust ANOVA results. Therefore, we reported separate non-parametric statistical outcomes when deemed feasible (i.e., adequate and balanced subgroup sample sizes) in an attempt to obtain as much information as possible about data trends and patterns. Because we were unable to capture within-subject correlations over time, as well as the treatment group*time interaction, our results should be interpreted accordingly.

The primary outcome was compliance with HDI and PEG IFN (i.e., percentage of doses taken based on total doses required over 53 weeks, as recorded in patient diaries), with a difference of 30% between groups deemed clinically relevant. We reported frequencies and percentages per week and an overall percentage of doses taken at the end of 53 weeks, with statistical analysis of this outcome.

Secondary outcomes were as follows (with different time points reported depending on the highest outcome frequencies):

- Comparison of the convenience and satisfaction with chemotherapy for patients on standard HDI versus PEG IFN using a chemotherapy convenience and satisfaction questionnaire (CCSQ), summation of items CS1 – GP5, with a 30% between-group difference deemed clinically relevant. Time points of comparison were baseline/week 1, week 3, week 13, week 25, and week 50.
- Item GF7, which assesses contentment with current quality of life, at baseline/week 1, week 3, week 13, week 25, and week 49.
- Item CS10, which assesses satisfaction with current results of chemotherapy, at week 1, week 3, week 13, week 25, week 37, and week 45.
- Items CS11 and CS12, which measure recommendation/choice of chemotherapy regimen, at week 1, week 3, week 13, week 25, week 37, and week 45.
- Item CS13, which rates the chemotherapy regimen overall, at week 1, week 3, week 13, week 25, week 37, and week 45.

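### Under the SAP's 53-week compliance ratio, a dose in a week with no returned diary cannot be told apart from a missed dose, and no rule says how such weeks are scored

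*SAP*

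**What the plan says.** The SAP (Data Analysis, primary outcome) measures compliance as "percentage of doses taken based on total doses required over 53 weeks, as recorded in patient diaries". It reports weekly figures and one overall percentage at the end of the 53 weeks, tests that overall figure with p below .05 as the criterion, and treats a 30% difference between groups as relevant.

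Protocol 9.1 describes the same endpoint as the "percentage of doses taken (as recorded in the diary) over the treatment period as prescribed by the physician". It has no 53-week denominator.

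On how dose data arrive, protocol 6.8 states: "The diaries will be returned to the Investigator at the subsequent visit". The synopsis adds an end-of-study visit within 21 days of stopping study treatment: "Final diary collection, safety assessments, treatment perceptions and HRQOL evaluations will be conducted at this visit". No infusion record, pharmacy record or dosing form is named as a source for this endpoint. Section 6 lets sites adapt the schedule of assessments to local practice and exempts only the quality-of-life questionnaires, so the diary has no such protection.

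On leaving the study, protocol 5.4 says "Patients will receive commercially available product". Section 5.4.1 treats withdrawal from the study separately from stopping interferon: "They may be considered withdrawn if they state an intention to withdraw, or fail to return for visits, or become lost to follow up".

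On missing data, protocol section 9 says that there will be no imputation and that missing points will be recorded and examined for patterns. The SAP says that missing data at the planned time points were too common, and apparently not random, for the planned ANOVA of the primary and two secondary outcomes. It does not give the amount.

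**The concern.** With a fixed denominator and a diary-only numerator, the ratio mixes three things: doses not taken, diaries not returned, and patients no longer followed. Supply is commercial and study withdrawal is separate from stopping treatment, so a patient can leave the study and stay on drug. Later doses then have no route into the numerator but remain in the denominator. The end-of-study diary collection is timed from stopping treatment, so such a patient does not clearly trigger it.

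At stake is the meaning of the primary result. Patients choose their treatment, the recording burden differs between regimens, and the SAP itself reports prevalent, apparently non-random missingness. If diary return differs between arms, the literal ratio shows that difference as a difference in drug compliance. The outcome is tested, and the study is meant to inform whether a larger trial is warranted.

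**Working it through.** The plan gives no compliance figure or derived sample size to reproduce, so the check is dose arithmetic.

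**Inputs (protocol Table 1, suggested dosing)**
- HDI: 5 × 4 = 20 induction doses and 3 × 48 = 144 maintenance doses, total 164.
- PEG IFN: one dose per week, 53 doses if 53 weeks are counted.

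These totals are assumptions. Sites may modify dosing (protocol 5.1), and the suggested HDI schedule spans 4 + 48 = 52 weeks, so the SAP's 53 weeks of required doses is not fully explained.

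**Score of a patient who takes every dose but whose diaries stop after week w (w at least 4), literal SAP ratio**
- HDI: [20 + 3(w − 4)] / 164
- PEG IFN: w / 53

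| Diaries stop at | HDI | PEG IFN |
|---|---|---|
| Week 13 | 47/164 = 28.7% | 13/53 = 24.5% |
| Week 26 | 86/164 = 52.4% | 26/53 = 49.1% |
| Week 39 | 125/164 = 76.2% | 39/53 = 73.6% |

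If weeks without a diary leave both numerator and denominator, the same patient scores 100% in every row. The result is not sensitive to the exact total: with three further HDI doses in week 53, the week-26 score is 86/167 = 51.5%.

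**One lost 4-week maintenance diary, all else complete**
- HDI: (164 − 12)/164 = 152/164 = 92.7%
- PEG IFN: (53 − 4)/53 = 49/53 = 92.5%

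**Arm level, true adherence 100%, a fraction f of the arm losing diaries from week 26**
- Arm mean = 1 − f(1 − s), where s is the week-26 score. Here 1 − s is 78/164 = 0.476 (HDI) and 27/53 = 0.509 (PEG IFN).
- f = 10%: 95.2% (HDI), 94.9% (PEG IFN).
- f = 40%: 81.0% (HDI), 79.6% (PEG IFN).
- Equal loss in both arms therefore opens a gap of at most about 1.4 points over this range.

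**Loss confined to one arm**
- Each 10% of the arm lost lowers its mean by 0.10 × (1 − s): at week 26, 4.8 points (HDI) or 5.1 (PEG IFN); at week 13, 7.1 or 7.5.
- A false 30-point gap needs f = 0.30/(1 − s): at week 26, about 63% (HDI) or 59% (PEG IFN) of the arm; at week 13, about 42% or 40%.

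All values of f are assumptions; the documents give no loss rates.

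**The case against.** The strongest reply is that no rule in either document scores an unreturned diary as zero. Protocol section 9 rules out imputation, and counting unknown doses as not taken could itself be called imputation. The SAP's weekly percentages could also be based on available diaries. This stands in part: the zero score follows from the literal ratio and is not a stated rule. But excluding weeks or patients would depart from the 53-week denominator that the SAP states, so the result turns on an unstated choice.

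Other limits also stand. A reader might infer that such a patient is labelled non-compliant. The documents have no such category: compliance is a percentage without a cut-off, and doses already recorded still count. A reader might infer that the last diary before leaving is always lost. The end-of-study visit includes a final collection, although its timing is tied to stopping treatment and so does not cover every withdrawal. A reader might also set section 5.4.1, where patients who "fail to return for visits, or become lost to follow up for any other reason" may be considered withdrawn, against section 6, which says "Visits falling outside this window should not lead to automatic patient discontinuation". These concern different events, absent visits and late or early ones, and do not conflict.

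Finally, the only driver of early exit that the protocol's background describes is toxicity leading to discontinuation. Those are permanent stops, which this point does not concern. No passage shows how many patients left while still on drug. The study is an exploratory pilot, and the SAP already asks for caution because of missing data. That caution, however, concerns the lost repeated-measures analysis and does not say how the compliance percentage treats missing diaries.

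**Conclusion.** The concern holds as a gap in the definition of the primary endpoint. Read literally, the SAP ratio counts doses of unknown status as not taken; protocol 9.1 has a different denominator; and no scoring rule reconciles them. For an individual the effect can be large: full adherence becomes roughly a quarter of doses if diaries stop at week 13 and about half if they stop at week 26. A single lost diary matters little, about 7 points. These figures rest on the suggested schedule and on full adherence after the diaries end.

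The documents do not support a specific false gap between arms. For example, if 30% of one arm and 10% of the other left while fully adherent, spread evenly over the year and losing about 49 points each on average, the gap would be about 0.20 × 49 = 10 points. Those rates are assumed, and equal rates would nearly cancel. A spurious 30-point gap would need about 40% or more of one arm lost by week 13. The defect therefore makes the primary result ambiguous; it does not show that the result is wrong or in which direction.

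**What to change.** The SAP is dated July 2023 and written in the past tense, so the useful changes are to the analysis of data already collected:

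1. Reconcile the denominators in protocol 9.1 and the SAP, show how the required doses over 53 weeks are counted in each arm, and state the rule for weeks without a diary.
2. Class each required dose as taken, not taken (including doses after a documented permanent stop) or unknown (no diary in a patient not known to have stopped).
3. Report by arm the percentage among known doses, bounds with all unknown doses set to taken and to not taken, and the number of diary-weeks missing. The bounds are needed because patients who stop returning diaries may also differ in adherence.
4. Where site source records already exist (protocol 8.1 requires sites to keep them), use them to confirm on-study HDI intravenous induction doses.

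As an illustration, a fully adherent HDI arm with 20% of patients losing diaries from week 26 would show 100% among known doses, with bounds of 90.5% (1 − 0.20 × 78/164) and 100%.

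The cost is one extra table, a limited check of existing records, and a wider range for the primary result. Two further steps suit a successor trial only: recording the date of last dose separately from the date of study withdrawal, and seeking permission at withdrawal to take later dosing from the medical record. The second carries real consent and abstraction costs.

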#### 6 Visit Schedule and Assessments

Table 2 and Table 3 are suggested assessments for both treatment arms and suggested visit procedures are indicated with an "x." This study schedule is a suggested guideline and can be modified per institutional standard practice guidelines, with the exception of QoL, which is mandatory at the time points as indicated.

Table 2: Schedule of Events Cohort A: HDI Suggested schedule of events (QOL evaluation is mandatory)

Test/Assessment	Pretreatment a	D1	D8 b	D15 b	D22 b	Maintenance Phase c
Informed consent	X					
Medical history	X					
Interferon preference questionnaire	X					
ECOG PS	X					
Weight/vital signs d		X	X	X	X	X
Physical examination e		X				X
Hematology labs f		X	X	X	X	X
Chemistry labs g		X	X	X	X	X
Collection and Monitoring of		X	X	X	X	X
Grade 3 and 4 AE and all SAEs h						
QoL evaluations i		X		X		X
Drug administration diary j		X	X	X	X	X

Treatment: Induction Phase: Suggested dosing per package insert is 20 million IU/m² IV infusion over 20 minutes, 5 consecutive days per week for 4 weeks; Maintenance Phase: 10 million IU/m² SC injection 3 times per week for 48 weeks. Dosing can be modified per institutional guidelines.

- a Within 4 weeks (28 days) of starting HDI
- b For Days 8, 15, and 22, if HDI was delayed, the study assessment schedule for these dates will also be delayed
- c . Maintenance dose begins at day 29 and then monthly until last dose of HDI.
- d Weight should be obtained at baseline. Vital signs should be performed at each visit.
- e Physical examination should be performed monthly or according to institutional protocol.
- Hematology labs will be done as clinically indicated and will include hemoglobin, hematocrit, RBC count, WBC count, platelets, as well as total and differential neutrophil counts. Hematology labs should be performed weekly during the induction phase or according to institutional protocol.

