- g Chemistry labs will be done as clinically indicated and should include albumin, creatinine kinase (CPK), urea or blood urea nitrogen (BUN), creatinine, alanine aminotransferase (ALT), aspartate aminotransferase (AST), lactate dehydrogenase (LDH), serum alkaline phosphatase, direct and total bilirubin, glucose, total protein, sodium, potassium, chloride, bicarbonate (HCO3) (CO2; venous blood), calcium, and phosphorous. Chemistries should be performed weekly during the induction phase or according to institutional protocol. Specific individual chemistry labs may be omitted according to investigator judgment if not included in the institution's chemistry profile.
- h All Grade 3 and 4 adverse events (regardless of whether they occur on treatment or non-treatment weeks) will be collected until the last day of treatment and submitted utilizing the corresponding AE forms. Additionally, all SAEs, regardless of grade will also be collected.
-  Treatment perceptions and HRQOL data will be collected via CCSQ and FACT-BRM, respectively, at baseline, every 2 weeks during the induction phase, and monthly during the maintenance phase (beginning at day 29) for up to 1 year. These questionnaires are to be completed prior to the administration of the dose for that visit. If dose is held or changed QoL is still to be completed.
- j Patients will be instructed to record details on the receipt of HDI in the drug administration diary and will return the diary to the site at the subsequent visit. These diaries will capture the onset of AEs in relationship to the day of drug administration.

Table 3: Schedule of Events (Cohort B: PEG IFN) Suggested schedule of events (QOL evaluation is mandatory)

Test/Assessment	Pretreatment a	D1	D8 b	D15 b	D22 b	b	b	b	Maintenance Phase c
Informed consent	X								
Medical history	X								
Interferon preference questionnaire	X								
ECOG PS	X								
Weight/vital signs d		X	X	X	X				X
Physical examination e		X							X
Hematology labs f		X	X	X	X				X
Chemistry labs g		X	X	X	X				X
Collection and Monitoring of		X	X	X	X				X
Grade 3 and 4 AE and all SAEs h									
QoL evaluations i		X		X					X
Drug administration diary j		X	X	X	X				X

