Treatment: Induction Phase: Suggested dosing per package insert is 6 mcg/kg/week SC for 8 doses (8 weeks); Maintenance Phase: 3 mck/kg/week SC injection for up to 5 years (this study will only evaluate the first year of treatment). Dosing can be modified per institutional guidelines.

- a Within 4 weeks (28 days) of starting PEG IFN
- b For Days 8, 15, 22, 29, 36, 43, and 50 if PEG IFN was delayed, the study assessment schedule for these dates will also be delayed
- Maintenance dose begins at day 29 and then monthly until last dose of PEG IFN, or until treatment discontinuation or one year of therapy
- d Weight should be obtained at baseline. Vital signs should be performed at each visit.
- e Physical examination should be performed monthly or according to institutional protocol.
- Hematology labs will be done as clinically indicated and will include hemoglobin, hematocrit, RBC count, WBC count, platelets, as well as total and differential neutrophil counts.. Hematology labs should be performed weekly during the induction phase or according to institutional protocol.
- g Chemistry labs will be done as clinically indicated and should include albumin, creatinine kinase (CPK), or urea blood urea nitrogen (BUN), creatinine, alanine aminotransferase (ALT), aspartate aminotransferase (AST), lactate dehydrogenase (LDH), serum alkaline phosphatase, direct and total bilirubin, glucose, total protein, sodium, potassium, chloride, bicarbonate (HCO3) (CO2; venous blood), calcium, and phosphorous. Chemistries should be performed weekly during the induction phase or according to institutional protocol. Specific individual chemistry labs may be omitted according to investigator judgment if not included in the institution's chemistry profile.
- h All Grade 3 and 4 adverse events (regardless of whether they occur on treatment or non-treatment weeks) will be collected until the last day of treatment and submitted utilizing the corresponding AE forms. Additionally, all SAEs, regardless of grade will also be collected.
- Treatment perceptions and HRQOL data will be collected via CCSQ and FACT-BRM, respectively, at baseline, 2 weeks, 4 weeks, 6 weeks, and monthly during the maintenance phase (beginning at Day 57) for up to 1 year. These questionnaires are to be completed prior to the administration of the dose for that visit. If dose is held or changed, QoL is still to be completed.

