- Treatment-related side effects that may impact the patient's health-related QoL (HRQOL) using the Functional Assessment of Cancer Therapy of Biologic Response Modifier (FACT BRM), with a 30% between-group difference in scores deemed clinically relevant. Time points of comparison were baseline/week 1, week 3, week 13, week 25, and week 50.

- The frequency of Grade 3 and 4 adverse events (AEs), according to the National Cancer Institute (NCI) Common Toxicity Criteria for Adverse Events (CTCAE) for patients on standard HDI versus PEG IFN, and the frequency of severe adverse events (SAEs), regardless of grade.
- Patients' reasons for their choice of treatment with HDI versus PEG IFN at the study's conclusion, for those cases in which patients were presented with a choice of either treatment option.

All analyses were conducted using IBM SPSS Statistics for Windows, Version 25.0 (Armonk, NY: IBM Corp.), with $p < .05$ denoting statistical significance.

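### The SAP shows CCSQ items CS10–CS13 at week 1, where the only scheduled form is pre-dose, and stops them at week 45, dropping every planned 12-month display, including CS13's only one

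*SAP*

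**What the plan says.** **Protocol, section 9 (Data Analysis).** CS10, CS11 and CS12 are to be described by treatment group at 2 weeks and at 3, 6 and 12 months. CS13 is to be described once, at the end of the study, which the protocol equates with 12 months. No baseline is planned for any of the four, although GF7 and the CS1–GP5 sum do have one. No inferential analysis is planned for GF7 or CS10–CS13.

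**Protocol, section 6 (Tables 2 and 3, footnote i).** The questionnaires may not be varied by site custom: the schedule is flexible "with the exception of QoL, which is mandatory at the time points as indicated". Forms fall at Day 1 and Day 15, and then for HDI "monthly during the maintenance phase (beginning at day 29) for up to 1 year". PEG IFN patients have further forms at 4 and 6 weeks, and then "monthly during the maintenance phase (beginning at Day 57) for up to 1 year". Each form is filled in before that visit's dose.

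**Protocol, Appendix 13.1.** CS10–CS13 sit under a stem that asks patients to draw on their chemotherapy experience so far.

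**SAP, secondary outcomes.** The weeks differ by outcome, "with different time points reported depending on the highest outcome frequencies". CS10 and CS11–CS12 are given the same six weeks as CS13: "Item CS13, which rates the chemotherapy regimen overall, at week 1, week 3, week 13, week 25, week 37, and week 45". For another item of the same questionnaire the list is different: "Item GF7, which assesses contentment with current quality of life, at baseline/week 1, week 3, week 13, week 25, and week 49". For the CS1–GP5 sum and for FACT-BRM: "Time points of comparison were baseline/week 1, week 3, week 13, week 25, and week 50". The SAP also says that the missing data "appeared not to be missing at random".

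**The concern.** Patients choose their interferon with their physician, so the arms may differ in expectation before any drug is given. If the week 1 answers come from the Day 1 form, an arm difference in CS10–CS13 at that week reflects expectation or misunderstanding of the question. It cannot reflect treatment experience. The SAP labels the first point of GF7, the CS1–GP5 sum and FACT-BRM as baseline/week 1, but uses plain week 1 for CS10–CS13. A reader would naturally take that as on-treatment.

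At the other end, the overall rating that the protocol wanted once, at the end of the year, is not shown at that time. An earlier week stands last in the list. Weeks were selected by a criterion that the SAP does not define, in data that it describes as not missing at random, and the last week differs from the one used for other items on the same form.

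**Working it through.** No sample size, power or alpha figure bears on this point. The check is a comparison of planned and reported displays plus day counts.

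**1. Planned against reported displays**

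| Item | Protocol section 9 | SAP weeks | Planned points kept | Planned points lost |
|---|---|---|---|---|
| CS10 | 2 wk, 3, 6, 12 mo | 1, 3, 13, 25, 37, 45 | 3 of 4 | 12 mo |
| CS11 | 2 wk, 3, 6, 12 mo | same | 3 of 4 | 12 mo |
| CS12 | 2 wk, 3, 6, 12 mo | same | 3 of 4 | 12 mo |
| CS13 | 12 mo | same | 0 of 1 | 12 mo |

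Planned: 3 × 4 + 1 = 13. Kept: 3 × 3 = 9 (weeks 3, 13 and 25 for CS10–CS12). Lost: 13 − 9 = 4, all at 12 months.

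**2. What is scheduled in week 1**

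Week 1 is Days 1–7. In both cohorts the CCSQ is due on Day 1 and next on Day 15, which is the first day of week 3. The only scheduled form in week 1 is therefore Day 1, and it is completed before the dose.

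**3. Where week 45 falls**

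Days from Day 1 to the start of week w = 7 × (w − 1).

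| Week | Days after Day 1 |
|---|---|
| 13 | 84 = 3 × 28 |
| 25 | 168 = 6 × 28 |
| 45 | 308 = 11 × 28 |
| 49 | 336 = 12 × 28 |
| 50 | 343 |
| 53 | 364 = 52 × 7 |

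The documents allow several meanings of 12 months:

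- twelve 28-day months (the spacing implied by weeks 13 and 25): 336 − 308 = 28 days after the start of week 45;
- the HDI course of 4 + 48 = 52 weeks, or the start of the last of the SAP's 53 weeks: 364 − 308 = 56 days after;
- a calendar year: 365 − 308 = 57 days after.

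The protocol's suggested maintenance window is ±7 days. Week 45 is outside it on every definition.

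**4. Whether later forms were due**

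Every 28 days from Day 29 (HDI), and every 28 days from Day 57 (PEG IFN), both give Days 309, 337 and 365, that is weeks 45, 49 and 53. With calendar months the last forms fall at about weeks 48 and 52 in both arms. On either reading a CCSQ form was due after week 45. The SAP's own lists show that CCSQ answers from weeks 49 and 50 are reported for other items.

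**5. Whether the protocol allowed the omission**

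Section 9 makes the 12-month point depend on the amount of missing data for the ANOVA outcomes: compliance, the CS1–GP5 sum and, by reference to that plan, FACT-BRM. No such condition is attached to CS10–CS13.

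**The case against.** - **The change is disclosed.** The SAP says that weeks varied with outcome frequency, that missing data were prevalent, and that results need cautious reading. This stands in part. It does not say that the 12-month displays were dropped or that week 1 is pre-dose, and it does not define the selection criterion.
- **Week 1 may not be the Day 1 form.** The SAP does not say which form it is, and the different label may be deliberate. A late form completed after dosing is possible, though none is scheduled. So the first step is to confirm the source. A reader might infer that all week 1 answers were pre-dose; the documents establish this only for the scheduled form.
- **12 months is not well defined.** This stands. A reader might infer that week 49 is the right 12-month week. The documents do not support that: week 49 starts 364 − 336 = 28 days before week 53, the HDI course lasts 52 weeks, and CS13 is tied to the end of the study. The Synopsis also requests an end-of-study visit within 21 days of stopping treatment, with treatment perceptions collected there. The documents allow about week 49 to week 53, and none of that range reaches back to week 45.
- **Extra descriptive weeks do no harm.** This stands too. A reader might count every display beyond the plan (24 − 9 = 15) as a departure. Nothing in section 9 forbids extra descriptive weeks, so the count carries no weight if they are labelled. What matters is the 4 missing displays and the meaning of week 1.
- **The stakes are low.** The CCSQ is not formally validated, the items are descriptive and the study is a pilot. Late answers depend on who is still on treatment at week 45 and at 12 months alike. A reader might infer that the choice of week 45 favours one arm; nothing in the documents shows that.

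**Conclusion.** The point holds. For CS10–CS13 the SAP adds a week 1 display for which the only scheduled form precedes the first dose, and it loses all 4 of the planned 12-month displays (4 of 13), including the only one for CS13. Week 45 falls 28 to 57 days short of 12 months, depending on the definition.

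The conclusion on week 1 assumes that the answers come from forms completed as scheduled, which the sponsor should confirm. The conclusion on 12 months needs no choice among the definitions. It does assume that the SAP's weeks are counted from Day 1, which fits weeks 3, 13 and 25.

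This limits what these four items can show. It does not touch the primary outcome, alpha or power, and no direction of bias is claimed. Weeks 3, 13 and 25 for CS10–CS12 match the plan.

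**What to change.** 1. State whether week 1 for CS10–CS13 is the Day 1 pre-dose form. If it is, remove it from the treatment comparisons or show it only as labelled pre-treatment data.
2. Report CS10–CS13 at the planned 12-month or end-of-study point with n per arm, even if sparse.
3. Use one stated 12-month window for all CCSQ items and FACT-BRM, reconciled with the 52-week HDI course, the SAP's 53 weeks and the end-of-study visit. Do not simply set it at week 49.
4. State how end-of-study forms are assigned to weeks, including those of patients who stop early. Section 5.4.1 ends all study procedures at permanent discontinuation, while the Synopsis asks these patients back for a visit, so the two need to be reconciled.
5. If weeks 37 and 45, and CS13 at weeks 3, 13 and 25, are kept, label them as unplanned. Define what is meant by highest outcome frequencies.
6. Say that CS10–CS13 remain descriptive. The SAP provides for non-parametric tests where feasible and does not repeat the protocol's exclusion of inference for these items.

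The cost is some SAP wording and a few descriptive tables re-run on forms already collected. The drawback is small numbers at 12 months, drawn from patients still on treatment or returning for the end-of-study visit. Giving n per arm at both week 45 and 12 months lets the reader judge that.
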